7.1.4 Supplier

The study will use commercial supply.

7.1.5 Dosage Form and Preparation

Pantoprazole Sodium Delayed-Release Tablets, USP are supplied as 40 mg white to off-white, oval-shaped, coated tablet, debossed with “17” on one side and are available as follows: Unit dose packages of 80 (8 x 10) NDC 68084-813-09.

7.1.6 Storage and Stability

Store Pantoprazole Sodium Delayed-Release Tablets, USP at 20° to 25°C (68° to 77°F); excursions permitted to 15° to 30°C (59° to 86°F).

7.1.7 Administration

Pantoprazole will be given at a dose of 40 mg once daily for up to 10 days (POD 1 through POD 10), or until discharge, whichever is earlier.

7.2 Placebo

Placebo capsules contain pharmaceutical-grade lactose monohydrate NF, a naturally occurring disaccharide of galactose bound to glucose. Lactose monohydrate is a free-flowing, dry powder that is water soluble, inert, nontoxic, and chemically stable.

8.0 DATA SUBMISSION SCHEDULE

Case report forms with appropriate source documentation will be completed according to the schedule listed in this section.

Case Report Form	Submission Schedule
Original Consent Form	Prior to registration
On-Study Form Medical History Form	Prior to starting treatment
Surgery Form Randomization Form	Time of surgery
Treatment Form	End of treatment
Post-Operative Form	Day 30 Post-Op
Post-Operative Complication Form	Day 14 Post-Op Day 30 Post-Op Day 90 Post-Op
90-Day Follow-Up Form	Day 90 Post-Op
Adverse Event Form	End of treatment Day 14 Post-Op Day 30 Post-Op Day 90 Post-Op
Toxicity Form	Start of treatment through 30 days after discontinuation of PPI/placebo

8.1 Adverse Event Collection in the Case Report Forms

All adverse events that occur beginning with start of treatment (minus exceptions defined in Section 6.0) must be captured in the Post-Operative Complication Form. Baseline AEs should be captured on the Medical History Form.

9.0 DATA AND SAFETY MONITORING

In compliance with the Washington University Institutional Data and Safety Monitoring Plan, an independent Data and Safety Monitoring Board (DSMB) will be specifically convened for this trial to review toxicity data. A DSMB will consist of no fewer than 3 members including 2 clinical investigators and a biostatistician. DSMB members must be employed by Washington University, Barnes-Jewish Hospital, or St. Louis Children's Hospital. Like investigators, DSMB members are subject to the Washington University School of Medicine policies regarding standards of conduct. Individuals invited to serve on the DSMB will disclose any potential conflicts of interest to the trial principal investigator and/or appropriate university officials, in accordance with institution policies. Potential conflicts that develop during a trial or a member's tenure on a DSMB must also be disclosed.

The DSM report for the DSMB will be prepared by the study team with assistance from the study statistician, will be reviewed by the DSMB, and will be submitted to the Washington University

Quality Assurance and Safety Monitoring Committee (QASMC). The DSMB must meet at least every six months beginning six months after accrual has opened (if at least one patient has been enrolled), no more than one month prior to the due date of the DSM report to QASMC. This report will include:

- HRPO protocol number, protocol title, Principal Investigator name, data coordinator name, regulatory coordinator name, and statistician
- Date of initial HRPO approval, date of most recent consent HRPO approval/revision, date of HRPO expiration, date of most recent QA audit, study status, and phase of study
- History of study including summary of substantive amendments; summary of accrual suspensions including start/stop dates and reason; and summary of protocol exceptions, error, or breach of confidentiality including start/stop dates and reason
- Study-wide target accrual and study-wide actual accrual
- Protocol activation date
- Average rate of accrual observed in year 1, year 2, and subsequent years
- Expected accrual end date and accrual by cohort
- Objectives of protocol with supporting data and list the number of participants who have met each objective
- Measures of efficacy
- Early stopping rules with supporting data and list the number of participants who have met the early stopping rules
- Summary of toxicities separated by cohorts
- Abstract submissions/publications
- Summary of any recent literature that may affect the safety or ethics of the study

Further DSMB responsibilities are described in the DSMB charter.

The study principal investigator and coordinator will monitor for serious toxicities on an ongoing basis. Once the principal investigator or Research Patient Coordinator becomes aware of an adverse event, the AE will be reported to the HRPO and QASMC according to institutional guidelines.

Refer to the Washington University Quality Assurance and Data Safety Monitoring Committee Policies and Procedures for full details on the responsibilities of the DSMB. This is located on the QASMC website at <https://siteman.wustl.edu/research/clinical-research-resources/protocol-office-prmcqasmc/>.

10.0 STATISTICAL CONSIDERATIONS

This is a randomized placebo-controlled study. Patients who will undergo pancreaticoduodenectomy at Washington University in St. Louis/Barnes-Jewish Hospital will be randomized on a 1:1 basis to receive either PPI or placebo.

10.1 Statistical Hypotheses

10.1.1 Primary Objective and Endpoint

The primary objective is to determine the effect of PPIs on the incidence of delayed gastric emptying within 90 days in patients after pancreaticoduodenectomy. The primary endpoint is the incidence of post-operative delayed gastric emptying using the ISGPS criteria and MAGS grading.

10.1.2 Secondary Objectives and Endpoints

1. Determine the effect of PPIs on the incidence of overall postoperative complications in the patients after pancreaticoduodenectomy.
2. Determine the marginal ulcer free survival (MUFS) within 90 days after surgery in the patients undergoing pancreaticoduodenectomy.

Secondary endpoints include: the incidence of surgical complication defined by the modified accordion grading system and MUFS.

10.2 Sample Size Determination

For primary endpoint, our preliminary study showed that the rates of delayed gastric emptying in the control the PPI groups are 7% and 21%, respectively. 110 patients per group achieve 80.4% power to detect a 14% difference between two groups using the two-sided Fisher's Exact test at the significance level of 5%.

For the endpoint of surgical complication, our preliminary study showed that the rates in the control the PPI groups are 56% and 74%, respectively. 120 patients per group achieve 80.0% power to detect a 18% difference between two groups using the two-sided Fisher's Exact test at the significance level of 5%.

The preliminary data show approximate 27% of randomized patients did not receive at least one dose of study treatment (PPI/placebo) and were replaced. We will randomize 330 patients in order to obtain 80% power for these two endpoints and account for possible 27% drop-out. We estimate that 12 patients per month would be eligible for the trial and the enrollment could be complete within 36 months.

10.3 Randomization

Three hundred thirty patients will be randomized on a 1:1 basis to receive either PPI or placebo. A computer-generated randomization scheme with a various block size will be used to assign patients. It is maintained centrally by the study statistician. Randomization will take place after surgery in REDCap.

10.4 Population for Analyses

10.4.1 Efficacy Analyses Set

The Intent-to-Treat (ITT) population will consist of all randomized patients.

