Study Description:	This is a randomized placebo-controlled study of patients who will undergo pancreaticoduodenectomy at Washington University in St. Louis/Barnes-Jewish Hospital. The study aims to determine the impact of administration of Proton Pump Inhibitors (PPIs) on the postoperative course in these patients. Postoperative administration of PPI and no intervention are both considered standard of care approaches.
Objectives:	
Primary Objective: Determine the effect of PPIs on the incidence of delayed gastric emptying within 90 days in patients after pancreaticoduodenectomy.
 
Secondary Objectives:
 
 • Determine the effect of PPIs on the incidence of overall postoperative complications in the patients after pancreaticoduodenectomy. • Determine the marginal ulcer-free survival (MUFS) within 90 days after surgery in the patients undergoing pancreaticoduodenectomy.
Endpoints:	
Primary Endpoint: Incidence of delayed gastric emptying using the ISGPS criteria and MAGS grading.
 
Secondary Endpoints:
 
 • Incidence of surgical complication defined by the Modified Accordion Grading System. • MUFS.
Study Population:	Two hundred forty patients who will undergo standard of care pancreaticoduodenectomy and receive at least one dose of study treatment (PPI/placebo) at Washington University/Barnes-Jewish Hospital
Phase:	II
Description of Sites / Facilities Enrolling:	This study will take place at Washington University School of Medicine and associated hospitals/clinics.
Description of Study Intervention:	Immediately post-op, patients will be randomly assigned to one of the two standard of care approaches (“PPI” or “placebo”) on a 1:1 basis in a blinded fashion. Patients will be initiated on pantoprazole or a visually equivalent placebo once daily from Postoperative Day 1 and continued for 10 doses or until the day of discharge (whichever is earlier).
Study Duration:	39 months
Participant Duration:	90 days

SCHEMA

SCHEDULE OF ASSESSMENTS

Measure	Baseline ²	Pre-op Visit ³	Day of Surgery	Post-op Visit ⁴	90 Days Post-Op
Confirmation of surgical plan	X				
Patient consent			X ⁵		
Medical history		X			
Randomization			X ⁶		
Demographics captured from EMR ¹		X			
Drug/placebo administration			X ⁷		
Notes from surgery related hospitalization captured from EMR				X	
Information on surgical complications captured from EMR/HPB Whipple Database					X

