4.5 Measures to Minimize Bias: Randomization and Blinding

Randomization will occur in the research pharmacy using a computer-generated randomization sequence. Consenting patients will be randomly assigned to receive pantoprazole or an identical appearing placebo in a 1:1 ratio. Medications will be prepared by the pharmacy and delivered to the treating nurse. The research team and the study participants will be blinded to treatment assignment.

Post-operative oral doses will be dispensed in identical capsules; active capsules will contain an over-encapsulated pantoprazole 40 mg delayed-release tablet with lactose monohydrate backfill and placebo capsules will contain lactose monohydrate to give equal weight and feel.

The research pharmacy will maintain documentation of medication procurement and preparation, as well as randomization, dispensing, and accountability logs. All medications and blinding supplies will be stored in a secure location within the research pharmacy and maintained under controlled environmental conditions.

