5.0 STUDY PROCEDURES

We have set our criteria to review any pancreaticoduodenectomies with gastric/biliary reconstruction performed as definitive management for a benign or malignant disease in the Department of Surgery at Washington University/ Barnes Jewish Hospital.

Written consent will be obtained from the patients at their preoperative visit or at time of admission to BJH for pancreaticoduodenectomy. Patients may have their surgery postponed for up to 6 months and will be given the option to continue participation in the study. Subjects that decide to continue to participate will continue to be eligible for participation.

Immediately post-op, the patients will be randomly assigned to the “PPI” or “placebo” groups in a 1:1 ratio as described in Section 4.5. The patients will be initiated on pantoprazole or a visually equivalent placebo once daily from Postoperative Day 1 and continued for 10 doses or until the day of discharge (whichever is earlier). Other postoperative management will be performed as per institutional standard of care.

Any patient who appears to require administration of a PPI secondary to a postoperative indication, i.e. stress ulcer prophylaxis in ICU, gastrointestinal bleeding, will discontinue trial treatment and initiated on the indicated PPI. These participants will not be unblinded, nor will they be replaced.

The patients will be followed as per standard of care to record incidence of any postoperative complications, including marginal ulcers. There are no follow-up visits mandated by participation in this protocol. Patients' medical records will be reviewed to collect information about complications for 90 days post-op. The division's Whipple database will also be used to collect information regarding post-operative complications.

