5.1 Definitions of Evaluability and Patient Replacement

Endpoint	In order to be evaluable for this endpoint, a patient must have...
Primary: Incidence of delayed gastric emptying using the ISGPS criteria and MAGS grading	Received at least one dose of study treatment (PPI/placebo)
Secondary: Incidence of surgical complication defined by MAGS grading criteria	
Secondary: Marginal ulcer-free survival	

Note: Patients who do not receive at least one dose of study treatment (PPI/placebo) are inevaluable for the primary endpoint and will be replaced. Patients who receive a PPI secondary to a postoperative indication will not be replaced.

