APPENDIX F: Study-Specific DSM Tables

Protocol Objectives and Subject Evaluability	
Objective	# of patients evaluable for this endpoint to date
Primary	
Determine the effect of PPIs on the incidence of delayed gastric emptying within 90 days in patients after pancreaticoduodenectomy.	
Secondary	
Determine the effect of PPIs on the incidence of overall postoperative complications in the patients after pancreaticoduodenectomy.	
Determine the marginal ulcer-free survival (MUFS) within 90 days in the patients undergoing pancreaticoduodenectomy.	

Interim Analysis and Early Stopping Rules	
Does the study design include an interim toxicity analysis?	
No	
Does the study design include an interim futility analysis?	
No	
Are there early stopping rules that outline circumstances under which the study must be suspended or closed?	
No	

Response and Survival							
UPN	On tx date	# doses	Pt replaced? (y/n)	Delayed gastric emptying? (y/n)	Off tx reason	Vital status	If dead, cause

Summary of Specimen Collections			
Type of specimen	Time point	# of patients eligible for collection at this time point	% of patients who have reached this time point and had the specimen collected
N/A (no research specimens collected on this study)

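### The primary efficacy set is defined in two incompatible ways (all 330 randomized, or about 240 dosed), and the power statement fits only the dosed set

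*Combined protocol and SAP*

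**What the plan says.** Section 10.4.1, headed as the efficacy set, names a single population: "The Intent-to-Treat (ITT) population will consist of all randomized patients". Sections 10.2 and 10.3 put the number randomized at 330.

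Other sections work from a different population:

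- Section 5.1 makes one dose of study treatment the condition for evaluability and adds: "Patients who do not receive at least one dose of study treatment (PPI/placebo) are inevaluable for the primary endpoint and will be replaced".
- The Protocol Summary describes the study population as "Two hundred forty patients who will undergo standard of care pancreaticoduodenectomy and receive at least one dose of study treatment (PPI/placebo)".
- Section 10.2 reports: "The preliminary data show approximate 27% of randomized patients did not receive at least one dose of study treatment (PPI/placebo) and were replaced". It then sets the total: "We will randomize 330 patients in order to obtain 80% power for these two endpoints and account for possible 27% drop-out".
- The monitoring tables in Appendix F ask, for each objective, for the number "of patients evaluable for this endpoint to date".

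Sections 10.5.2 and 10.5.3, which describe the primary and secondary analyses, do not name a population. No section ranks the two rules or labels one of them as a sensitivity analysis.

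**The concern.** A patient who is randomized after surgery but never takes a capsule is in the analysis under Section 10.4.1 and out of it under Section 5.1. By the plan's own estimate this applies to more than a quarter of those randomized. Two analysts who each followed the text could report the primary result on different patients, and nothing stops the choice from being made once the data are known.

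There are two further consequences. Staff who follow Section 5.1 may not collect 90-day outcomes for patients regarded as replaced, and the intention-to-treat (ITT) analysis would then be impossible. Also, Section 10.2 enlarges the trial as if never-dosed patients leave the analysis. Under ITT they stay in and dilute the treatment contrast.

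**Working it through.** **Inputs.** Section 10.2 gives delayed gastric emptying (DGE) rates of 7% (control) and 21% (PPI), complication rates of 56% and 74%, a two-sided Fisher's exact test at 5%, 110 per group for DGE (stated power 80.4%), 120 per group for complications (stated power 80.0%), 27% never dosed and 330 randomized. Section 10.3 gives 1:1 allocation, so 165 per arm. Fisher power was computed by full enumeration of both binomial distributions.

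**Step 1: the plan's own figures.**

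- DGE at 110 per group: 82.4% exact, against 80.4% stated. The continuity-corrected normal formula gives exactly 110 per group for 80% power.
- Complications at 120 per group: 80.4% exact, against 80.0% stated.
- Inflation: 2 × 120 / (1 − 0.27) = 240/0.73 = 329, against 330 stated.

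Section 10.2 is therefore sound for dosed patients. With 120 dosed per arm, DGE power is 85.6% and complications power 80.4%.

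**Step 2: size of the disagreement.** 330 × 0.73 = 241 dosed, and 330 − 241 = 89 randomized but never dosed (27%).

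**Step 3: power for the set in Section 10.4.1.** The documents give no event rate for never-dosed patients, so an assumption is needed: 27% never dosed in each arm, with the same risk *u* in both arms and hence no treatment contrast among them. Then

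arm risk = 0.73 × dosed risk + 0.27 × *u*.

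At control risk:

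- DGE (*u* = 7%): control 7%; PPI 0.73 × 21% + 0.27 × 7% = 17.2%.
- Complications (*u* = 56%): control 56%; PPI 0.73 × 74% + 0.27 × 56% = 69.1%.

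Power at 165 per arm, two-sided 5%:

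| Endpoint | *u* | Fisher | Score | Wald log-OR |
|---|---|---|---|---|
| DGE | 0% | 84.0% | 88.7% | 87.6% |
| DGE | 3.5% | 80.8% | 85.8% | 84.6% |
| DGE | 7% | 77.9% | 82.9% | 81.7% |
| DGE | 14% | 72.6% | 77.4% | 76.7% |
| DGE | 21% | 67.9% | 72.7% | 72.3% |
| DGE | 30% | 62.7% | 67.6% | 67.0% |
| Complications | 30% | 64.0% | 68.1% | 68.1% |
| Complications | 40% | 64.1% | 68.2% | 68.2% |
| Complications | 56% | 65.3% | 69.3% | 69.1% |
| Complications | 74% | 68.8% | 72.7% | 72.4% |
| Complications | 95% | 73.7% | 77.4% | 77.0% |

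As an upper bound, with no dilution at all, Fisher power at 165 per arm would be 95.2% (DGE) and 91.7% (complications). That would require never-dosed patients to show the full drug effect.

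**Step 4: what 330 can detect under ITT.** With Fisher's test at 165 per arm, 80% power corresponds to about 10.5 points from a 7% control rate and about 15.4 points from 56%. The diluted differences at control risk are 14 × 0.73 = 10.2 points and 18 × 0.73 = 13.1 points.

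**Step 5: what would restore 80% at control risk.** 172 per arm (344 in total) for DGE and 228 per arm (456) for complications. Section 10.2 expects 12 eligible patients a month for 36 months: 12 × 36 = 432.

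**The case against.** **Bias from the exclusion is unlikely.** Capsules are identical, and Section 4.5 says "The research team and the study participants will be blinded to treatment assignment". Leaving the study before the first dose should therefore not depend on the arm, and a dosed-only comparison could be defended. This stands. The fault is that the analysis is not fixed; bias has not been shown.

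**Dosed-only may be what is intended.** Section 5.1, the Summary and Section 10.2 all lean that way, and only Section 10.4.1 says ITT. Choosing the dosed set would also end the contradiction and keep the power figures. This stands as an alternative, but Section 10.4.1 would have to be rewritten and the set could not be called ITT.

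**The ITT power loss is modelled.** The documents do not give the rate on which it depends, and all cases in the table assume no contrast among never-dosed patients. That is the natural assumption for people who took no study drug, but it remains an assumption. For DGE the result also depends on the test: at control risk the score and Wald versions exceed 80%, and Section 10.5.2 plans odds ratios and logistic regression, not Fisher's test. A shortfall on the primary endpoint is therefore not established. The firm shortfall is on complications, a secondary endpoint.

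**Some of the evidence and cost is slight.** Appendix F is a monitoring template and defines no analysis set. Section 5.0 already provides that "medical records will be reviewed to collect information about complications for 90 days post-op", with no dosing condition, so follow-up of never-dosed patients may need only confirmation.

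None of these points reconciles Section 10.4.1 with Section 5.1.

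**Conclusion.** The concern holds and must be fixed. The population for the primary analysis is undetermined for about 89 of 330 randomized patients. That conclusion needs only the plan's text and its 27% figure.

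The 80% power claimed for both endpoints belongs to the dosed set. Under ITT, with 27% never dosed in each arm and no contrast among them, complications power is 64% to 74% by Fisher's test and stays below 80% under all three tests. DGE power by Fisher's test runs from 84% down to 63% as the never-dosed rate rises from 0% to 30%. Near control risk it lies on either side of 80%, depending on the test.

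**What to change.** Before unblinding:

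1. Name one primary efficacy set and make the Summary, Sections 5.1, 10.2, 10.4.1, 10.5.2 and 10.5.3, and Appendix F agree with it. The preferred choice is ITT, all randomized patients as assigned, because Section 10.4.1 already says so.
2. Remove the evaluability and replacement rule for efficacy from Section 5.1. Patients already regarded as replaced stay in the ITT set.
3. State that never-dosed patients are included in the 90-day record review unless they withdrew consent.
4. Report the at-least-one-dose analysis as a labelled supplementary analysis.
5. Restate Section 10.2 for 165 randomized per arm, giving the assumption and the range: about 78% (DGE) and 65% (complications) by Fisher's test at control risk, with the score or Wald figures beside them (83% and 82% for DGE; 69% for complications under either). Alternatively, give the detectable differences of about 10.5 and 15.4 points.

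If the sponsor prefers a dosed-only primary set, Section 10.4.1 must be rewritten to say so and the ITT label dropped; the Section 10.2 figures can then stay.

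The cost is protocol wording, record review for about 89 patients within a process that already exists, and a less favourable power statement. No extra patients are proposed. Restoring 80% for complications under ITT at control risk would need 456 patients, more than the 432 eligible patients that Section 10.2 implies. That comparison would remain underpowered for the assumed 18-point effect, and the plan should say so.
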